9.5.1.4.2 PHARMACODYNAMIC, PHARMACOGENOMIC, AND OTHER BIOMARKER ASSESSMENTS

Blood samples, archived tumor tissue samples, and fresh tumor tissue by biopsy will be collected for pharmacodynamic and pharmacogenomic assessment. PD-1 and other relevant biomarkers identified by the new perception or progress of science will be assessed, if needed. Biomarker discovery will be performed to identify pharmacological effect and to predict subject response to lenvatinib and nivolumab as well as for potential use in diagnostic development.

9.5.1.4.2.1 Blood Biomarker

Blood samples for the development of exploratory biomarkers will be collected from all consented subjects at designated time points as specified in the Schedule of Procedures/Assessments (Table 9) (blood samples for nivolumab will be collected in Part 2 only). Instructions for the processing, storage, and shipping of samples will be provided separately in the Laboratory Manual.

9.5.1.4.2.2 Tissue Biomarker

Archival tumor tissue must be provided for biomarker analysis as well as for potential use in diagnostic development if available (Part 1 and Part 2).

In Part 2, if archival tumor tissue is not available, a newly obtained tumor tissue by fresh biopsy must be available prior to the first dose of study drug for biomarker analysis (fresh biopsy is not mandatory for the subject with previous tumor tissue or with inaccessible tumors of safety concern). Instructions for the processing, storage, and shipping of samples will be provided separately in the Laboratory Manual.

Security of the samples, use of the samples, retention of the samples, and subject privacy are provided below.

Security of the Samples, Use of the Samples, and Retention of the Samples

Sample processing, for example DNA extraction, genotyping, sequencing, or other analysis will be performed by a laboratory under the direction of the sponsor. Processing, analysis, and storage will be performed at a secure laboratory facility to protect the validity of the data and maintain subject privacy.

Samples will only be used for the purposes described in this protocol. Laboratories contracted to perform the analysis on behalf of the sponsor will not retain rights to the samples beyond those necessary to perform the specified analysis and will not transfer or sell those samples. The sponsor will not sell the samples to a third party.

Samples will be stored for up to 15 years after the completion of the study. At the end of the storage period, samples will be destroyed. Samples may be stored longer if a Heath Authority (or medicinal product approval agency) has active questions about the study. In this special circumstance, samples will be stored until the questions have been adequately addressed.

Right to Withdraw

If, during the time the samples are stored, a participant would like to withdraw his/her consent for participation in this research, the sponsor will destroy the samples. Information from any assays that have already been completed at the time of withdrawal of consent will continue to be used as the results of the research project.

Subject Privacy and Disclosure of Data

Samples will be single coded (Subject ID number). No subject-identifying information (eg, initials, date of birth, government identifying number) will be associated with the sample.

The sponsor will take steps to ensure that data are protected accordingly and confidentiality is maintained as far as possible. The sponsor and its representatives and agents may share coded data with persons and organizations involved in the conduct or oversight of this research. These include:

- Medical institutions
- Clinical research organizations retained by the sponsor
- Independent ethics committees or institutional review boards that have responsibility for this research study
- National regulatory authorities or equivalent government agencies

At the end of the analysis, results may be presented in the clinical study report or a separate report which can include part or all of the coded data, in listing or summary format. Other publication (eg, in peer-reviewed scientific journals) or public presentation of the study results will only include summaries of the population in the study, and no identified individual results will be disclosed.

9.5.1.4.3 ANTI-NIVOLUMAB ANTIBODIES

Table 7 presents the detailed blood sampling schedule for anti-nivolumab antibodies. Anti-nivolumab antibodies will be quantified using a validated method. If an anti-nivolumab antibody develops, presence of neutralizing antibody will be detected. See the Laboratory Manual for a description of collection, handling, and shipping procedures for samples.

Table 7 Blood Sampling Schedule for Anti-nivolumab Antibodies

Day	Sampling Time	Allowance (As a Target)
Cycle 1 Day 1	Predose of nivolumab	Within –60 minutes before dosing
Cycle 1 Day 15	Predose of nivolumab	Within –60 minutes before dosing
Cycle 2 Day 1	Predose of nivolumab	Within –60 minutes before dosing
Cycle 3 Day 1	Predose of nivolumab	Within –60 minutes before dosing
Cycle 5 Day 1	Predose of nivolumab	Within –60 minutes before dosing
Cycle 9 Day 1	Predose of nivolumab	Within –60 minutes before dosing
Cycle 13 Day 1	Predose of nivolumab	Within –60 minutes before dosing
Thereafter Day 1 of every 4 cycles	Predose of nivolumab	Within –60 minutes before dosing

9.5.1.5 Safety Assessments

Safety assessments include monitoring and recording all AEs, including all grading of CTCAE v4.03, and SAEs; regular laboratory evaluation for hematology, blood chemistry, and urine values; physical examinations; periodic measurement of vital signs; ECGs; and echocardiograms/MUGA scans to assess LVEF.

9.5.1.5.1 ADVERSE EVENTS

An AE is any untoward medical occurrence in a subject. An AE does not necessarily have a causal relationship with the medicinal product. For this study, the study drugs are lenvatinib and nivolumab.

The criteria for identifying AEs in this study are:

- Any unfavorable and unintended sign (including an abnormal laboratory finding), symptom, or disease found after the time of informed consent, whether or not considered related to the investigational product (Note: Every sign or symptom should not be listed as a separate AE if the applicable disease [diagnosis] is being reported as an AE)
- Any new disease or exacerbation of an existing disease. However, worsening of the primary disease should be captured under efficacy assessments as disease progression rather than as an AE.
- Any deterioration in nonprotocol-required measurements of a laboratory value or other clinical test (eg, ECG or x-ray) that results in symptoms, a change in treatment, or discontinuation of study drug
- Recurrence of an intermittent medical condition (eg, headache) not present pretreatment (Baseline)
- An abnormal laboratory test result should be considered an AE if the identified laboratory abnormality leads to any type of intervention, withdrawal of study drug, or withholding of study drug, whether prescribed in the protocol or not

All AEs, regardless of relationship to study drug or procedure, should be collected beginning from the time the subject signs the study ICF through the 30 days after the last dose or until the subject initiates new anticancer therapy, whichever is earlier. SAEs will also be collected for 30 days after the last dose or until the subject initiates new anticancer therapy, whichever is earlier.

Any laboratory abnormality considered to constitute an AE should be reported on the CRF. Abnormal laboratory values should not be listed as separate AEs if they are considered to be part of the clinical syndrome that is being reported as an AE. It is the responsibility of the investigator to review all laboratory findings in all subjects and determine if they constitute an AE. Medical and scientific judgment should be exercised in deciding whether an isolated laboratory abnormality should be classified as an AE.

Abnormal ECG (QTcF) results, if not otherwise considered part of a clinical symptom that is being reported as an AE, should be considered an AE if the QTcF interval is more than

450 ms and there is an increase of more than 60 ms from baseline. Any ECG abnormality that the investigator considers as an AE should be reported as such.

Progression of malignant disease (PD) should not be recorded as an adverse event in studies where it is included as an endpoint for underlying disease. If the progression leads to an untoward medical occurrence (increased pain, pleural effusion, etc.), then this medical occurrence should be the adverse event.

All AEs must be followed until 30 days after the last dose or until resolution, whichever comes first. All SAEs must be followed to resolution or, if resolution is unlikely, to stabilization.

Every effort must be made by the investigator or subinvestigator to categorize each AE according to its severity and its relationship to the study treatment.

Assessing Severity of Adverse Events

Adverse events will be graded on a 5-point scale according to CTCAE v 4.03. Investigators will report CTCAE grades for all AEs (for both increasing and decreasing severity).

Assessing Relationship to Study Treatment

Items to be considered when assessing the relationship of an AE to the study treatment are:

- Temporal relationship of the onset of the event to the initiation of the study treatment
- The course of the event, especially the effect of discontinuation of study treatment or reintroduction of study treatment, as applicable
- Whether the event is known to be associated with the study treatment or with other similar treatments
- The presence of risk factors in the study subject known to increase the occurrence of the event
- The presence of nonstudy, treatment-related factors that are known to be associated with the occurrence of the event

Classification of Causality

The relationship of each AE to the study drug will be recorded on the CRF in response to the following question:

Is there a reasonable possibility that the study drug caused the AE?

Yes (related) A causal relationship between the study drug and the AE is a reasonable possibility.

No (not related) A causal relationship between the study drug and the AE is not a reasonable possibility.

9.5.1.5.2 SERIOUS ADVERSE EVENTS AND EVENTS ASSOCIATED WITH SPECIAL SITUATIONS

An SAE is any untoward medical occurrence that at any dose:

- Results in death
- Is life-threatening (ie, the subject was at immediate risk of death from the adverse event as it occurred; this does not include an event that, had it occurred in a more severe form or was allowed to continue, might have caused death)
- Requires inpatient hospitalization or prolongation of existing hospitalization
- Results in persistent or significant disability/incapacity
- Is a congenital anomaly/birth defect (in the child of a subject who was exposed to the study drug)

Other important medical events that may not be immediately life-threatening or result in death or hospitalization but, when based on appropriate medical judgment, may jeopardize the subject or may require intervention to prevent one of the outcomes in the definition of SAE listed above should also be considered SAEs. Medical and scientific judgment should be exercised in deciding whether expedited reporting is appropriate in such situations.

In addition to the above, events associated with special situations include pregnancy or exposure to study drug through breastfeeding; AEs associated with study drug overdose, misuse, abuse, or medication error (see Section 9.5.4.2 and 9.5.4.3). These events associated with special situations are to be captured using the SAE procedures but are to be considered as SAEs only if they meet one of the above criteria. All AEs associated with special situations are to be reported on the CRF whether or not they meet the criteria for SAEs.

All SAEs must be followed to resolution or, if resolution is unlikely, to stabilization.

The following hospitalizations are not considered to be SAEs because there is no “adverse event” associated with the hospitalization:

- Hospitalizations for respite care
- Planned hospitalizations required by the protocol
- Hospitalization planned before informed consent (where the condition requiring the hospitalization has not changed after study drug administration)
- Hospitalization for administration of study drug or insertion of access for administration of study drug
- Hospitalization for routine maintenance of a device (eg, battery replacement) that was in place before study entry

9.5.1.5.3 LABORATORY MEASUREMENTS

Clinical laboratory tests to be performed, including hematology, chemistry, and urinalysis, are summarized in Table 8. The Schedule of Procedures/Assessments (Table 9) shows the visits and time points at which blood for clinical laboratory tests and urine for urinalysis will be collected in the study. Clinical laboratory tests will be performed at each site.

Table 8 Clinical Laboratory Tests

Category	Parameters
Hematology	RBC count, hemoglobin, hematocrit, platelets, and WBC count with differential (basophils, eosinophils, lymphocytes, monocytes, neutrophils)
Anticoagulant test	INR ^a
Chemistry	
Liver function tests	Alkaline phosphatase, aspartate aminotransferase, alanine aminotransferase, gamma glutamyl transpeptidase, total bilirubin, direct bilirubin
Renal function tests	Blood urea nitrogen, creatinine
Other	Glucose, albumin, total cholesterol, triglycerides, phosphorus, lactate dehydrogenase, total protein, sodium, potassium, chloride, calcium, magnesium, ammonia ^b , amylase ^c , lipase ^c , ACTH ^e , cortisol ^e
Tumor marker	AFP
Thyroid function tests	TSH, FT4
Virus tests ^b	HIV antibody, HCV antibody, HBs antigen, HBs antibody, HBc antibody, HBV DNA, HCV RNA, HDV antibody or HDV RNA ^d
Urinalysis	pH, protein, glucose, ketones, RBCs, specific gravity

AFP = α -fetoprotein, INR = International Normalized Ratio

a: INR will be assessed on C2D1 and every cycle thereafter.

b: Screening only. Data within 28 days before the first dose can be used.

c: Amylase and lipase will be measured at Screening, C2D1 and every cycle thereafter.

d: Subjects with hepatitis B only

e: If necessary, appropriate laboratory tests such as adrenal cortical function test (ACTH, cortisol) to be added.

A laboratory abnormality may meet the criteria to qualify as an AE as described in this protocol (see Section 9.5.1.5.1). In these instances, the AE corresponding to the laboratory abnormality will be recorded on the CRF. If AEs were assessed during unscheduled visits, all the data corresponding to the laboratory abnormality will also be recorded on the CRF.

9.5.1.5.4 VITAL SIGNS AND WEIGHT MEASUREMENTS

Vital sign measurements (ie, systolic and diastolic BP [mmHg], pulse [beats per minute], body temperature [in centigrade]), and weight (kg) and percutaneous oxygen saturation (SPO₂) will be obtained at the visits designated in the Schedule of Procedures/Assessments (Table 9) by a validated method. BP and pulse will be measured sitting after the subject has been resting. All BP measurements should be performed on the same arm, preferably by the same person.

Height will be measured at the Screening Visit only.

9.5.1.5.5 PHYSICAL EXAMINATIONS

Physical examinations will be performed as designated in the Schedule of Procedures/Assessments (Table 9). Documentation of the physical examination will be included in the source documentation at the site. Only changes from screening physical examination findings that meet the definition of an AE will be recorded on the CRF.

9.5.1.5.6 ELECTROCARDIOGRAMS

Electrocardiograms will be obtained as designated in the Schedule of Procedures/Assessments (Table 9). Standardized, 12-lead ECG recordings that permit all 12 leads to be displayed on a single page with an accompanying lead II rhythm strip below the customary 3×4 lead format may also be used. In addition to a rhythm strip, a minimum of 3 full complexes should be recorded from each lead simultaneously. Subjects must be in the recumbent position for a period of 5 minutes prior to the ECG.

An ECG abnormality may meet the criteria of an AE as described in this protocol (see Section 9.5.1.5.1). In these instances, the AE corresponding to the ECG abnormality will be recorded on the CRF.

9.5.1.5.7 ECHOCARDIOGRAM OR MULTIPLE GATED ACQUISITION SCAN

An echocardiogram or a MUGA scan (using technetium-99m-pertechnetate) to assess LVEF will be performed at Screening and at discontinuation visit. Echocardiograms or MUGA scans should be performed locally in accordance with the institution's standard practice. Either an echocardiogram or a MUGA scan which is used for an individual subject at baseline should be repeated for all subsequent LVEF assessments for that subject. LVEFs as assessed by the institution will be entered onto the CRF.

9.5.1.5.8 ECOG PS

An ECOG performance status should be done at each visit as designated in the Schedule of Procedures/Assessments (Table 9).

9.5.1.5.9 OTHER SAFETY ASSESSMENTS

9.5.1.5.9.1 Pregnancy Test

An hCG or β -hCG test will be performed for women of childbearing potential. A serum or urine sample will be taken at visits as designated in the Schedule of Procedures/Assessments (Table 9).

All females will be considered to be of childbearing potential except:

- Females who are postmenopausal (amenorrheic for at least 12 consecutive months without other known or suspected cause)
- Females who have been sterilized surgically (ie, bilateral tubal ligation, total hysterectomy, or bilateral oophorectomy, all with surgery at least 1 month before dosing)

- Females who have no possibility to be pregnant due to medical reasons

9.5.1.5.9.2 Viral Tests

Hepatitis B surface (HBs) antigen, HBs antibody, hepatitis B virus core (HBc) antibody, hepatitis C virus (HCV) antibody, HBV-DNA, HCV-RNA, HDV antibody or HDV RNA (hepatitis B only), and HIV antibody tests will be performed at Screening. Data within 28 days before the first dose can be used.

9.5.2 Schedule of Procedures/Assessments

9.5.2.1 Schedule of Procedures/Assessments

Table 9 presents the schedule of procedures/assessments for the study.

Table 9 Schedule of Procedures/Assessments in Study E7080-J081-117 (for Part 1 and Part 2)

Phase	Pretreatment		Treatment								Follow-up	
Period	Screening	Baseline ^b	Cycle 1				Cycle 2 or later				Discontinuation	Last observation visit ^q
Day	-14 to -4	-3 to -1	1	8 (±2)	15 (±2)	22 (±2)	1 ^l (±3)	8 ^m (±3)	15 (±3)	22 ^m (±3)	(+7)	30 days after last administration (+7)
Informed consent ^a	X											
Inclusion/exclusion	X	X										
Demographic	X											
Prior medications and complication	X											
ECOG-PS	X	X					X				X ^o	
Physical examination, Vital signs, SPO ₂ , Height ^b , Weight	X	X		X	X	X	X	X	X	X	X ^o	X
12-lead ECG	X	X			X		X				X ^o	
MUGA or echocardiogram	X										X ^o	
Gastroenterological endoscopy	X ^f											
Laboratory test ^c	X	X		X	X	X	X	X	X	X	X ^o	X
Pregnancy test	X	X									X ^o	
Child-Pugh score	X	X					X				X ^o	
Lenvatinib administration			Throughout									
Lenvatinib PK blood sampling			X ⁱ		X ⁱ		X ⁱ					
Nivolumab administration			X		X		X		X			
Nivolumab PK blood sampling			X ^s		X ⁿ		X ^t		X ^u		X	X
Anti-nivolumab antibodies (ADA) blood samples			X ⁿ		X ⁿ		X ^v				X	X
Lenvatinib PD biomarker blood sampling			X ⁿ		X ⁿ		X ⁿ					
Nivolumab PD biomarker blood sampling			X ^w				X ^w				X ^w	
Archival tissues ^d							X					
Biopsy ^e	X											
CT assessment/Tumor marker	X ^g						X ^j				X ^p	
Hospitalization				X ^k								
Survival												X ^r
Adverse event			Throughout									

Table 9 Schedule of Procedures/Assessments in Study E7080-J081-117 (for Part 1 and Part 2)

Concomitant medications/therapies	Throughout

C#D# = Cycle#/Day#, ECOG-PS = Eastern Cooperative Oncology Group performance status, INR= international normalized ratio, MUGA= multiple gated acquisition scan.
 
a: Screening assessment should be initiated after obtaining informed consent (Informed consent can be obtained within 28 days of first dose).
 
b: Height (Screening only)
 
c: Virus test (Screening only), Data within 28 days before the first dose can be used), Ammonia test (Screening only), Hematology, blood chemistry, urinalysis, blood coagulation tests, thyroid function test. If necessary, appropriate laboratory tests such as adrenal cortical function test (ACTH, cortisol) to be added.
 
d: Effort should be made to obtain during study. Exclude subjects without available archival tissues.
 
e: Only in Part 2. Exclude subjects with inaccessible tumors for biopsy of safety concern.
 
f: Data within 3 months before the first dose can be used (data before obtaining informed consent can also be used).
 
g: Data within 28 days before the first dose can be used (data before obtaining informed consent can also be used).
 
h: Regarding tests which are performed in both screening and baseline, if screening test is done 4 days before first dose, baseline tests are not required.
 
i: For Part 1, blood collection at predose, 1, 2, 4, 8, 24 hours postdose of Cycle 1 Day1 and Day 15, and predose of Day 1 of every cycle thereafter. However, blood collection is not required after Cycle 24. For Part 2, blood collection at 0.5 - 4 hours postdose of Cycle1 Day1, pre and 0.5 - 4 hours postdose of Cycle1 Day15 and predose of Cycles 2, 4, 6
 
j: CT assessments (including tumor marker assessment) will be performed every 8 weeks (Day 1 [± 7 days] in odd number cycle) from Day 1 of Cycle 1, or more frequently if disease progression is clinically indicated.
 
k: Subjects will be hospitalized until completion of Cycle 1 in Part 1. Outpatient is allowed after C1D15 when investigator or subinvestigator judges that the subject's safety is ensured.
 
l: +3 days in C2D1 (Part 1 only)
 
m: Cycle 3 or later, test items can be omitted only when investigator or subinvestigator judges that that the subject's safety is ensured.
 
n: Predose
 
o: Data within 7 days before discontinuation, if available, can be used as the discontinuation data.
 
p: Data within 28 days before off treatment, if available, can be used as the discontinuation data.
 
q: If a new anticancer agent needs to be immediately started due to deterioration in the subject's condition, the last observation visit can be conducted before 30 days after the last dose of the study drug has passed but prior to starting the new anticancer agent. If the last observation visit occurs within 7 days after study drug discontinuation, discontinuation data can be used as the last observation data.
 
r: Only in Part 2. Every 12 weeks (± 2 weeks) from last observation visit
 
s: Predose and just before completion of nivolumab administration
 
t: Predose of Cycles 2, 3, 4, 5, 9, 13 (thereafter every 4 cycles) and just before completion of nivolumab administration in Cycle 5
 
u: Predose of Cycle 5
 
v: Predose of Cycles 2, 3, 5, 9, 13 (thereafter every 4 cycles)
 
w: Part 2 only. Predose of Cycles 1 and 3. When the subject discontinues the study before sampling of Cycle 3, the sampling at discontinuation visit should be done.
	

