19. Subjects with any active, known, or suspected autoimmune disease, with the following exceptions:
 - 1) Subjects with vitiligo, type 1 diabetes mellitus, resolved childhood asthma or atopy are permitted to enroll.
 - 2) Subjects with suspected autoimmune thyroid disorders may be enrolled if they are currently euthyroid or with residual hypothyroidism requiring only hormone replacement.
 - 3) Subjects with psoriasis requiring systemic therapy must be excluded from enrollment
20. Any history of interstitial lung disease, and interstitial lung disease that is symptomatic or may interfere with the detection and management of suspected drug-related pulmonary toxicity

21. Subjects with a condition requiring systemic treatment with either corticosteroids (>10 mg/day prednisone equivalent) or other immunosuppressive medications within 14 days of study administration. Inhaled or topical steroids and adrenal replacement doses >10 mg/day prednisone equivalents are permitted in the absence of active autoimmune disease.
22. Subjects with meningeal carcinomatosis
23. Subjects with any current brain or subdural metastases
24. Subjects who are known to be positive for Human Immunodeficiency Virus (HIV).
25. History of clinically significant hepatic encephalopathy
26. Serious nonhealing wound, ulcer, or bone fracture
27. Any subject who cannot be evaluated by either triphasic liver computed tomography (CT) or triphasic liver magnetic resonance imaging (MRI) because of allergy or other contraindication to both CT and MRI contrast agents
28. Subjects being treated with drugs that strongly inhibit or induce CYP3A4 and that may be possibly used during this study.
29. Any medical or other condition which, in the opinion of the investigator or subinvestigator, would preclude participation in a clinical trial
30. Females who are breastfeeding or pregnant at Screening or Baseline (as documented by a positive beta-human chorionic gonadotropin [β -hCG] (or human chorionic gonadotropin [hCG] test). A separate baseline assessment is required if a negative screening pregnancy test was obtained more than 72 hours before the first dose of study drug (females who discontinued breastfeeding will be eligible).

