9.1.3.1 Pretreatment Phase

The Pretreatment Phase will involve obtaining informed consent, a screening assessment, and a baseline assessment. Screening will occur within 14 days before starting study drug administration after obtaining written informed consent. Informed consent will be obtained after the study has been fully explained to each subject and before the conduct of any screening procedures or assessments (informed consent can be obtained within 28 days of first dose). After screening assessments, the sponsor will be informed of eligibility of the patient by the investigator or subinvestigator. The baseline assessment will be conducted within 4 days before starting study drug administration in order to confirm that the patient meet the eligibility requirement before moving to the Treatment Phase.

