29. Any medical or other condition which, in the opinion of the investigator, would preclude participation in a clinical trial
30. Females who are breastfeeding or pregnant at Screening or Baseline (as documented by a positive beta-human chorionic gonadotropin [β -hCG] (or human chorionic gonadotropin [hCG] test). A separate baseline assessment is required if a negative screening pregnancy

test was obtained more than 72 hours before the first dose of study drug (females who discontinued breastfeeding will be eligible)

31. Women of childbearing potential or man of impregnate potential who don't agree that both the subject and her partner will use the following methods of contraception for periods from before informed consent to during the clinical study and 5 months later (for male subjects 30 days) from last administration of study drug. For contraception method, subject must agree to use any 2 of the following methods: vasectomy or condom for a male subject or partner, bilateral tubal ligation, diaphragm, intrauterine device, or use of oral contraception from at least 28 days before starting the study treatment for a female subject or partner.
32. Participants who have received a live/attenuated vaccine within 28 days of first dose of study drugs

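### Table 9 footnote h can waive the baseline pregnancy test in a case where exclusion criterion 30 requires it, and nothing in the protocol says which rule prevails

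*Protocol*

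**What the plan says.** Four places in the protocol bear on the timing of the pre-dose pregnancy test.

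- **Table 9 (section 9.5.2.1).** Screening runs from Day -14 to Day -4 and Baseline from Day -3 to Day -1. The pregnancy test is marked at both, and next at Discontinuation. Footnote h opens with "Regarding tests which are performed in both screening and baseline" and continues that "if screening test is done 4 days before first dose, baseline tests are not required". It exempts no test.
- **Exclusion criterion 30 (Synopsis and section 9.3.2).** The Synopsis reads: "A separate baseline assessment is required if a negative screening pregnancy test was obtained more than 72 hours before the first dose of study drug". Section 9.3.2 sets the same limit.
- **Section 9.5.1.5.9.1.** The "test will be performed for women of childbearing potential", and the section refers to Table 9 for the visits. It does not mention the 72-hour limit.
- **Section 9.1.3.1.** "The baseline assessment will be conducted within 4 days before starting study drug administration", with the purpose of confirming eligibility. Screening is placed within 14 days before dosing, with no Day -4 close. These windows differ from those in Table 9.

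**The concern.** Footnote h and exclusion 30 give opposite instructions for the same test in the same situation. A site that works from the schedule, as section 9.5.1.5.9.1 directs, finds express permission to omit the baseline test after screening 4 days before dosing. A site that works from the eligibility list finds that the test has to be repeated. No passage ranks one above the other.

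What is at stake is a safety check before first exposure. Pregnancy is an exclusion at entry, a ground for stopping treatment (section 9.3.3.1, item 4) and a ground for withdrawal (section 9.5.4.2). Table 9 schedules no pregnancy test between Baseline and Discontinuation. If the waiver is used, the screening result is therefore the last scheduled one until treatment ends.

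**Working it through.** The plan has no figure of its own to reproduce here. The check compares the age of a waived screening test at first dose with the 72-hour limit.

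**Inputs**
- Waiver condition: screening test 4 days before first dose (Table 9 footnote h).
- Limit: 72 hours (exclusion 30, Synopsis and section 9.3.2).
- Windows: Screening Day -14 to -4, Baseline Day -3 to -1, first dose Day 1 (Table 9).
- Day numbering: no Day 0, so Day -k lies k calendar days before Day 1. This is how the table's columns run, and it makes 4 days before dosing equal to Day -4.

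**Formula**
A test on Day -k is nominally 24k hours old at a Day 1 dose. Test and dose can each fall at any minute of their day, so at one-minute resolution the age runs from 24k - 1439/60 to 24k + 1439/60 hours, where 1439/60 = 23.98.

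| Test day | Nominal age (h) | Range (h) | Against 72 h |
|---|---|---|---|
| Day -3 | 72 | 48.02 to 95.98 | either side |
| Day -4 | 4 x 24 = 96 | 96 - 23.98 = 72.02 to 96 + 23.98 = 119.98 | always above |
| Day -5 | 120 | 96.02 to 143.98 | always above |

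**Table 9 taken literally.** The latest screening day is Day -4, and even its shortest interval exceeds 72 hours. Reading footnote h as within 4 days changes nothing while Table 9's window stands, because no screening day is later than Day -4.

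**Wider reading.** Suppose footnote h means within 4 days and section 9.1.3.1 allows screening right up to dosing. The waiver then covers tests from 0 to 96 hours old. Those of 72 hours or less satisfy exclusion 30; those of more than 72 and up to 96 hours do not. The conflicting part is (96 - 72)/96 = 0.25 of the window. That is a share of time, not of subjects.

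The two rules therefore conflict on either reading. The readings differ only in how often.

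**The case against.** The strongest reply is that eligibility is checked again at Baseline. Table 9 marks the inclusion/exclusion row at both visits, footnote h speaks of tests and not of the eligibility review, section 9.1.3.1 gives confirmation of eligibility as the purpose of the baseline assessment, and section 9.3 bars dosing of anyone who fails the criteria. A site that re-reads exclusion 30 at Baseline would meet the 72-hour limit and might reasonably let the specific rule override the general footnote. This stands as a partial safeguard. It relies on the site's interpretation, because the protocol states no order of precedence and its pregnancy-test section points only to Table 9.

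A second reply is that footnote h is loosely worded and means within 4 days. There is some support for this. On Table 9's windows every screening test is more than 72 hours old, so the conditional form of exclusion 30 makes most sense if later screening is possible, as section 9.1.3.1 allows. A reader might infer that every use of the waiver for this test breaches exclusion 30. That holds only on Table 9's literal windows; under section 9.1.3.1 it shrinks to tests more than 72 and up to 96 hours old.

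Third, in the text as extracted from the PDF the Baseline column carries marker b, whose footnote concerns height. Footnote h has no other anchor and states its own scope, so this is most likely a conversion artefact.

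Finally, few subjects are involved and no endpoint or estimate is shown to change. That limits the size of the problem but does not remove the contradiction.

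**Conclusion.** The protocol contradicts itself on the pre-dose pregnancy test. On Table 9's windows, with no Day 0, using the footnote h waiver for this test always leaves a result more than 72 hours old. On the wider reading the conflict covers a quarter of the 96-hour window. Only women of childbearing potential are affected. The documents give no number; 0 to 2 of the approximately 26 subjects is an assumption. Such a woman would also have to be screened at the triggering time, at a site that follows the footnote instead of the criterion.

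A reader might go further and infer that a woman dosed under the waiver meets an exclusion, must stop treatment as a major eligibility violation (section 9.3.3.1, item 2), or drops out of the DLT Analysis Set for a major deviation (section 9.7.1.2). The documents do not support this. Exclusion 30 concerns pregnancy documented by a positive test, or breastfeeding; a missed repeat breaches the procedural sentence within it and does not show that she is pregnant. The protocol does not define what counts as major, and SAP section 5.2.3 leaves the deviation criteria to be set before database lock.

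No view is taken here on which timing rule is right.

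**What to change.** The sponsor should:

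1. Reconcile footnote h, exclusion 30 and the windows in section 9.1.3.1 and Table 9, so that together they give one timing rule for the pre-dose pregnancy test.
2. State in footnote h whether the waiver covers the pregnancy test.
3. Cross-reference the reconciled rule in section 9.5.1.5.9.1, which at present points only to Table 9.

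The cost is a clause in a footnote, a cross-reference and alignment of the window wording. The Baseline column already provides for the test, so no new visit or procedure is needed. If enrolment is already complete, the sponsor should still record which passage applied, and check whether the waiver was used for this test, when deviations are identified before database lock under SAP section 5.2.3.
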